5.6.3. Additional Safety Assessments (if applicable)

Not Applicable

5.6.3.1. Clinical Laboratory Tests

Protocol-Required Safety Laboratory Assessments are documented in Appendix 2 of the CTP. A listing of all laboratory values (abnormal or graded, when available) will be made, restricted to participants with at least one laboratory abnormality.

An abnormality (toxicity grade or abnormality based on normal ranges) will be considered as emerging in a particular period if it is worse than the baseline value. If the baseline is missing, the abnormality is always considered emerging. A shift from 'abnormally low' at baseline to 'abnormally high' post baseline (or vice versa) is also emerging. If a laboratory test result is censored (no numeric value is available, but only a verbatim term), a numeric value will be imputed by a value exceeding the cut-off value with one unit. (<x: subtract 1 unit from x, >x: add 1 unit to x; <3.45 is imputed with 3.44).

If no toxicity grades are defined for a test, the abnormalities (above/below normal range) will be used. In determining toxicity grades, the following rules are applied:

- Worst grades/abnormalities are determined over the whole observational period for each trial period separately, including all post-baseline measurements of that period.
- The abnormalities 'abnormally low' and 'abnormally high' are considered equally important, i.e. if a participant has as well an abnormally low as an abnormally high value post-baseline, both abnormalities are shown in the tables. (This means that the sum of the percentages can be more than 100%)
- The grading scale for some parameters in the grading table contains gaps (zones where no toxicity grade definition exists). In these cases, laboratory results falling in these gap zones will be allocated to the adjacent worst-case grade.
- If a lab value falls within the grading as specified in the grading table but also within the local lab normal limits, the value is considered normal.

No distinction will be made in grading for sample test results obtained under fasting and non-fasting conditions. If limits under fasting and non-fasting conditions differ, the limits of the condition (fasting/non-fasting) of scheduled visits as planned in the CTP will be used. The same applies to samples obtained under a different condition (e.g. samples of withdrawal visits).

5.6.3.2. Vital Signs and Physical Examination Findings

Physical examination findings will be summarized at baseline. A listing of the abnormalities will be made.

Vital signs including body temperature, pulse/heart rate, respiratory rate, and blood pressure (systolic and diastolic) will be summarized over time, using descriptive statistics. Abnormalities emerging after vaccination will be tabulated by worst abnormality grade using the FDA table in appendix 10.

A listing of participants with pyrexia/fever according to the FDA grading table will be provided. In addition, temperature measurements (whether obtained from the diary or from on-site assessments) will be allocated to predefined temperature intervals (from 37.5° C to 40°C, in half degree increments, e.g., <37.5; 37.5 to <38; 38 to <38.5; ... >40, and tabulated.

5.6.3.3. Other Safety Parameters

Not Applicable.

5.7. Other Analyses

Not applicable

5.7.1. Immunogenicity

5.7.1.1. Immunogenicity Analysis

The analysis of immunogenicity will use the PPI and NI analyses sets. Selected immunogenicity analyses may also be done on the FAS. Within each Cohort (Cohort 1 (Ad26.COV2.S primary vaccination); Cohort 2 (BNT162b2 primary vaccination)), data will be analyzed by vaccine group, and by vaccine group and participant seropositivity status at screening. Data will be presented by scheduled time point. Selected results will be presented in the same output with both cohorts.

For the PPI analysis, samples taken outside of the allowed window will be excluded from the tables and graphs (but will be included in the listings and clearly marked as results not included in the PPI analyses). For the FAS analysis, samples taken outside of the window will be included.

5.7.1.2. Parameters

Planned humoral and cellular immune assays are listed in the CTP section 8.1.4. However, not all assays might be available for all immunogenicity analyses covered by this SAP. Further information on which assays will be analyzed in each of the analyses, will be included in the corresponding DPS document(s).

5.7.1.3. Handling of Missing and/or Unquantifiable Immune Response Data

Missing immune response data will not be imputed.

Values below the lower limit of quantification (LLOQ) or limit of detection (LOD) will be handled as follows:

- Calculation of geometric mean and median:
 - o values <LLOQ(or LOD) are imputed with LLOQ(or LOD)/2.
- Calculation of fold increases from baseline or other reference timepoint:
 - o values <LLOQ(or LOD) are imputed with LLOQ(or LOD).

Values above the upper limit of quantification (ULOQ) will be handled as follows:

- Calculation of geometric mean and median:
 - o Values >ULOQ are imputed with ULOQ.
- Calculation of fold increases from baseline or other reference timepoint:
 - o Values >ULOQ are imputed with ULOQ.

5.7.1.4. Handling of changes in assay status throughout the study conduct

In case of changes in assay status, from “qualified” to “validated”, the LLOQ and ULOQ are likely to change as well. If this should happen, then the SDTM database will contain records pertaining to the assay in the qualified status and records pertaining to the validated status, and the LLOQ and ULOQ values will also differ.

The statistical analysis will use the LLOQ and ULOQ values associated with the validated assay and will retrospectively apply these on all the data pertaining to the assay, including the data obtained while the assay status was “qualified”. This may imply that data received, statistically analyzed, and presented at an earlier time may change. Graphical displays will show the eventually used LLOQ and ULOQ values. Graphs and tables will have an additional footnote that reflects the assay status. Immune Response Analysis

5.7.1.5. NI Analysis – Success Criterion and Statistical method

Formal NI testing in Cohort 1 will be conducted as a “within-participants” analysis, in which participants’ VNA data are considered matched pairs across the two time points. However, the formal NI testing in Cohort 2 will be conducted as between participant analysis comparing COV2008 Pfizer cohort (cohort 2) vs. the external Pfizer samples VNA data.

For each Primary objective in Cohort 1 and Cohort 2, the NI tests will be performed on the NI analysis set and must be demonstrated on both co-primary endpoints as well as on the GMR estimate criterion to conclude NI:

- GMR
- Responder rate for Cohort 1 and seropositivity rate for cohort 2
- An estimated GMR (GMT Day 15 post-booster/GMT post primary regimen) of >0.8

The primary responder definition (FDA) (see section 5.7.1.6.2.1) will be used for the NI assessment of the primary objectives.

Furthermore, hierarchical testing will be applied to the NI hypotheses in the cohorts (see CTP section 9.1; Figure 3: Decision Tree-based Hypothesis Testing).

In addition to the hierarchical NI hypotheses testing results, forest plot of responder rate (cohort 1) and seropositivity rate (cohort 2) differences and GMRs associated with the NI Hypotheses will be presented by cohort. The forest plots will also be presented by age group (see section 5.7.2).

The success criterion and the corresponding statistical methods to be used are as described below for each cohort.

Remark: Note that, in general, the lower bound of a 2-sided $100 * (1 - 2 * \alpha)\%$ CI (where $\alpha = 1$ -sided significance level) is equivalent to the lower bound of the 1-sided $100 * (1 - \alpha)\%$ CI which is needed for the NI hypothesis testing.

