The GMT induced in group k ($k = 5, 7$, or 8) is NI as compared to the GMT induced in group R3 using a NI margin of $2/3$. Similarly, the GMT induced in group k ($k = 6$) is NI as compared to the GMT induced in group R4 using a NI margin of $2/3$

Statistical method:

Objectives 2a, 2b, 2c and 2d: evaluated only at the primary analysis

The NI analysis on the GMR, in each group g ($g = 5, 7$, or 8) compared to the reference group R3 and in group $k=6$ compared to the reference group R4, will, respectively, be assessed by first constructing the 2-sided $(1 - 2*\alpha)$ % confidence interval for the difference in means (i.e., booster vaccination after Ad26.COV2.S (original virus or leading variant of high consequence or concern*) minus primary vaccination (original strain or leading variant of high consequence or concern*) log10 transformed data) based on the sampling distribution of two independent normal distributions with variances that are unknown but assumed equal.

Let $X_g = \log_{10} Y_g \sim N(\mu_g, \sigma_g)$, normally distributed with true population mean and standard deviation, μ_g and σ_g respectively and where X_g is the log-transformed (log₁₀ scale) virus neutralization assay (VNA) titers for Cohort 2 booster vaccine groups, $g = 5, 6, 7, 8$ (so defined to reflect the hypotheses in Figure 3 Refer to Clinical Trial Protocol (CTP); section 9.1).

Let $X_R = \log_{10} Y_R \sim N(\mu_R, \sigma_R)$, where X_R ($R = R_3$ or R_4) is the log-transformed (log₁₀ scale) virus neutralization assay (VNA) titers for the 2-dose Pfizer BNT162b2 primary vaccination (original strain) (Reference group 3) or the 2-dose Pfizer BNT162b2 primary vaccination (leading variant of high consequence or concern*), if feasible (Reference group 4)

It can be shown that the log-transformed (log₁₀ scale) virus neutralization assay (VNA) titers mean differences between the vaccine groups g , $(\bar{X}_g - \bar{X}_R)$, is equal to the log-transformed (log₁₀ scale) ratio of the corresponding geometric means, i.e., $\log_{10}(GMT_g/GMT_R)$

Hence, back transforming yields, $GMT_g/GMT_R = 10^{(\bar{X}_g - \bar{X}_R)}$ as the geometric mean ratio estimates.

Next, we can construct the $(1 - 2*\alpha)\%$ confidence interval (2-sided) (where $\alpha = 1$ -sided significance level), for the geometric mean ratios, by first constructing the confidence interval on the difference on the means, $(\bar{X}_g - \bar{X}_R)$.

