Assuming unknown equal variances for the population cohort 2 booster vaccine groups g and the reference group, R, and log-transformed (log₁₀ scale) virus neutralization assay (VNA) titers, the (1 - 2* α) % confidence interval (2-sided), (where α = 1-sided significance level), estimate for the population mean differences, is given by,

$$(\overline{X_g} - \overline{X_R}) \pm t_{(1-2*\alpha/2; v_p)} S_p \sqrt{\left(\frac{1}{n_g} + \frac{1}{n_R}\right)}$$

Where the *pooled variance estimate*, $S_p^2 = \frac{(n_g-1)S_g^2 + (n_R-1)S_R^2}{n_g+n_R-2}$ and $v_p = n_g + n_R - 2$ is the degrees of freedom for the t-distribution and $\alpha = 0.025$.

Since log transformation is monotone, back transforming confidence intervals for the difference in means in the log10 scale gives a confidence interval for the ratio of the geometric means. Hence, the lower and upper bounds of the 2-sided (1 - 2 * α)% (i.e., 97.5% since $\alpha = 0.0125$ (1-sided)) confidence interval for the GMT ratios are as follows:

$$((GMT\ Ratio))_{Lower\ Limit} = 10^{\left((\overline{X_g} - \overline{X_R}) - t_{(1-\alpha/2; v_p)} S_p \sqrt{\left(\frac{1}{n_g} + \frac{1}{n_R}\right)} \right)}$$

$$((GMT\ Ratio))_{Upper\ Limit} = 10^{\left((\overline{X_g} - \overline{X_R}) + t_{(1-\alpha/2; v_p)} S_p \sqrt{\left(\frac{1}{n_g} + \frac{1}{n_R}\right)} \right)}$$

If the assumptions of the unknown equal variances for the independent normal distributions of cohort 2 booster vaccine groups g and the reference group, R, do not hold (i.e., test of equality variances shows that the variances are significantly different), then an approximate t-distribution with Satterthwaite approximated degrees of freedom will be used instead (Casella, G & Berger L.R (1990)).

For each of the booster vaccine groups, g comparisons, NI will be demonstrated if

$((GMR\ Ratio))_{Lower\ Limit} > \frac{2}{3}$, where the lower limit corresponds to a 97.5% 2-sided confidence interval.

SAS v 9.4 will be used in implementing the NI comparisons.

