Within each vaccination group, Day 15 minus Day 0 responder rate differences will be estimated by transforming the model LSMEAN (in SAS) estimates on the logit scale to probability estimates. The associated 2-sided confidence intervals (95% CI for primary objective 1a and 97.5% CI for primary objectives 1c and 1d) will be determined using the bootstrap Percentile Confidence Interval method. A bootstrap sample of 10,000 will be generated with replacement from the original data to accomplish this. NI will then be declared if the within each vaccination group, lower limit of the 2-sided confidence intervals (95% CI for primary objective 1a and 97.5% CI for primary objectives 1c and 1d) of the responder rate (Day 15 – Day 0) difference is greater than -10% (see DPS for some guidance in coding).

Similarly, for the analysis each vaccination group repeated correlated continuous VNA data, Mixed Effects model method will be used. The random effects model will include the continuous log VNA (\log_{10} scale) variable as the dependent variable, day as fixed effects and subject as the random (repeated measures) effect. Unstructured variance-covariance matrix will be used in the model. PROC Mixed (in SAS) will be used to fit the model.

Within each vaccination group, Day 15 minus Day 0 mean differences (\log_{10} scale) and associated 2-sided confidence intervals (95% CI for primary objective 1a and 97.5% CI for primary objectives 1c and 1d) will be determined from the appropriate LSMESTIMATE (in SAS) of the vaccine day fixed effect in the model.

The GMRs (booster/primary) and associated confidence intervals will then be estimated by back transforming the differences in means (\log_{10} scale) and associated confidence intervals, respectively. NI, within a vaccination group, will then be declared if the lower limit of the 2-sided confidence interval (95% CI for primary objective 1a and 97.5% CI for primary objectives 1c and 1d) of the GMR (booster/primary) is greater than 2/3 (see DPS for some coding guidance).

Remark: Sensitivity analysis will only be conducted at the primary analysis.

5.7.1.6. Immunogenicity against the insert**5.7.1.6.1. Humoral assays****5.7.1.6.2. Responder Definition and Data Summary**

For neutralizing and binding antibodies to the reference SARS-CoV-2 strain and variants:

- A sample will be considered positive if the value is strictly greater than the LLOQ ($>\text{LLOQ}$).

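### The mandatory GMR estimate above 0.8 is missing from the cohort-level success criteria, and the Cohort 2 decision sentence, read literally, concludes non-inferiority without it

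*SAP*

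**What the plan says.** Section 5.7.1.5 gives the general rule. For each primary objective in Cohort 1 and Cohort 2, NI "must be demonstrated on both co-primary endpoints as well as on the GMR estimate criterion". Three bullets follow: the GMR, the responder rate (Cohort 1) or seropositivity rate (Cohort 2), and "An estimated GMR (GMT Day 15 post-booster/GMT post primary regimen) of >0.8". The section then refers the reader to the cohort sections for the success criterion and the methods.

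Sections 5.7.1.5.1 and 5.7.1.5.2 each contain a Success Criterion 1 (rate difference, margin -10%) and a Success Criterion 2 (GMR, margin 2/3). Neither has a third criterion, and 0.8 does not appear again.

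The Cohort 2 method ends with a decision sentence: "For each of the booster vaccine groups, g comparisons, NI will be demonstrated if" the lower limit of the GMR exceeds 2/3, "where the lower limit corresponds to a 97.5% 2-sided confidence interval". Section 5.7.1.5.1 has no closing sentence of this kind.

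The Cohort 1 sensitivity analysis (5.7.1.5.3) has two separate NI declarations. One rests on the lower limit of the responder rate difference exceeding -10%. The other rests on the lower limit "of the GMR (booster/primary) is greater than 2/3". Neither mentions the point estimate.

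**The concern.** A programmer who builds the decision from the numbered criteria would leave out the 0.8 condition. One who builds it from the general section would include it. For a precise Cohort 2 result with a GMR a little below 0.8, the first would report NI and the second would not. This is a primary conclusion, and section 5.7.1.5 places these hypotheses in a hierarchical testing scheme, so the verdict on one hypothesis can decide whether the next is tested. Section 5.8.1 shows the same dependence in Cohort 1: hypothesis 1b is tested at the interim only if every success criterion of 1a is met, yet only two are numbered.

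A sensitivity analysis with a looser rule than the analysis it supports could also appear to confirm a result that the primary rule rejects.

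**Working it through.** **Wording.** In its criterion 1 paragraph, section 5.7.1.5.2 keeps two ideas apart. When one criterion is satisfied, it says that this criterion has been met for the hypothesis. When the hypothesis fails, it says that NI has not been demonstrated. The sentence after the GMR interval uses the second, hypothesis-level form. By then seropositivity has already acted as a gate, so the sentence reads as the last step, and 0.8 is not in it.

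**The plan's own figure.** The interval level for the Cohort 2 GMR is 1 - 2 × 0.0125 = 0.975, which reproduces the stated 97.5%.

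**When the rules differ.** The lower-limit rule passes any estimate above

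(2/3) × 10^(t × SD × √(1/n_g + 1/n_R)).

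The 0.8 condition adds something only if the interval's half-width on the log10 scale is below log10(0.8 / (2/3)) = log10(1.2) = 0.0792.

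**Inputs.** From the SAP: margin 2/3, point-estimate threshold 0.8, 97.5% two-sided interval, n_R about 300. Assumed, because the SAP does not give them: a common log10 SD of 0.3 to 0.5 and n_g of 200, 300 or 330. The value 330 is borrowed from Cohort 1 Group 1, where section 5.8.1 puts 110 at about 33% of the total.

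**SD below which the rules can disagree**, 0.0792 / (t × √(1/n_g + 1/300)):

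| n_g | t (0.9875) | √(1/n_g + 1/300) | SD cut-off |
|---|---|---|---|
| 200 | 2.248 | 0.0913 | 0.386 |
| 300 | 2.247 | 0.0816 | 0.432 |
| 330 | 2.247 | 0.0798 | 0.442 |

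**Smallest GMR that passes the 2/3 rule, 330 against 300:**

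| SD | Half-width (log10) | Smallest passing GMR | Disputed range |
|---|---|---|---|
| 0.3 | 0.0538 | 0.755 | 0.755 to 0.80 |
| 0.4 | 0.0717 | 0.786 | 0.786 to 0.80 |
| 0.5 | 0.0896 | 0.819 | none |

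With 200 boosted participants the smallest passing GMR is 0.768 at SD 0.3 and 0.805 at SD 0.4, so the conflict has already gone at 0.4.

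**How often.** With 330 against 300 and a true GMR of exactly 0.80, the chance that the estimate falls in the disputed range is about 36% at SD 0.3, 9% at SD 0.4 and 0% at SD 0.5. This is a normal approximation with SD treated as known and the seropositivity gate taken as passed.

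**A related ambiguity.** Section 5.7.1.5.2 prints one-sided alpha as both 0.025 and 0.0125, with two different t subscripts (1 - 2α/2 and 1 - α/2). Depending on the pairing, the interval is 95%, 97.5% or 98.75%, and the SD cut-off at 330 against 300 is 0.505, 0.442 or 0.396. The table uses the stated 97.5%.

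**Sensitivity analysis.** No figure is given. It pools post-primary data over three arms in a mixed model, and the SAP has no inputs from which to rebuild its standard error.

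**The case against.** The general section expressly covers Cohort 2 and uses mandatory wording, and nothing in the cohort sections withdraws it. The Cohort 2 sentence closes the method for Success Criterion 2, so it can be read as deciding that component only. As a complete rule standing alone it would drop seropositivity too, which the same section makes a gate. The two sensitivity sentences are clearly per endpoint, since each ignores the other. The SAP also leaves the hypotheses and decision tree to protocol section 9.1, which may state the full rule.

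Most of this stands. A reader might infer that the 0.8 condition was dropped for Cohort 2, or that the SAP contains complete, weaker decision rules. The text does not show that. It shows a general rule and a decision sentence that do not agree as written. A reader might also infer that the sensitivity analysis could open the next step of the hierarchy. Nothing in 5.7.1.5.3 feeds its result into the hierarchy, and the general rule does not name that analysis.

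The objection does not remove the defect. The general section sends the reader to the cohort sections for the success criterion, those sections count two, and the Cohort 2 sentence uses the phrase that the same section reserves for the hypothesis as a whole.

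**Conclusion.** The point holds as an unresolved inconsistency in a primary decision rule. The 0.8 condition is mandatory in 5.7.1.5, absent from the numbered criteria of both cohorts, and absent from a Cohort 2 sentence that literally concludes NI. In Cohort 1 the general section remains the only full decision statement, so there the defect is an omission from the list.

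It would be too strong to say that NI would be declared at GMRs the general rule rejects. In Cohort 2 it could be, and only if the log10 SD is below about 0.39 (200 boosted) to 0.44 (330 boosted) against about 300 external samples at 97.5%. The disputed band is then at most a few hundredths of a GMR unit over the SDs examined (0.755 to 0.80 at SD 0.3), and at SD 0.5 it is empty. SD and booster arm size are assumptions. The conclusion rests on the SAP text alone.

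**What to change.** - In 5.7.1.5.1 and 5.7.1.5.2, add a Success Criterion 3: the estimated GMR is above 0.8.
- In 5.7.1.5.2, reword the sentence after the GMR interval to say that a lower limit above 2/3 means success criterion 2 is met.
- End each cohort section with one decision sentence: NI is concluded for a hypothesis only if all three criteria are met.
- In 5.7.1.5.3, replace the two per-endpoint NI declarations with one conclusion that uses the same three conditions as the primary rule.

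The cost is SAP wording and a matching check of the output specifications. No new data, analysis or sample size is needed, because the GMR estimate is already produced with its interval.

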5.7.1.5.1. Cohort 1 (primary objectives 1a,1b,1c and 1d)

To assess the 4 NI hypotheses related to Cohort 1 (CTP section 9.1), the neutralizing antibody response 14 days post Ad26.COV2.S booster vs the neutralizing antibody response 28 days post primary vaccination with Ad26.COV2.S will be used.

For the NI analysis, define the following groups:

- 1 = Ad26.COV2.S 5×10^{10} vp booster after Ad26.COV2.S (original virus)
- 2 = Ad26.COV2.S 5×10^{10} vp booster after Ad26.COV2.S (leading variant of high consequence or concern*), if feasible
- 3 = Ad26.COV2.S 2.5×10^{10} vp booster after Ad26.COV2.S (original virus)
- 4 = Ad26.COV2.S 1×10^{10} vp booster after Ad26.COV2.S (original virus)

R1 = Ad26.COV2.S 5×10^{10} vp primary vaccination (original strain) – (Reference group 1)

R2 = Ad26.COV2.S 5×10^{10} vp primary vaccination (leading variant of high consequence or concern*), if feasible (Reference group 2)

Success Criterion 1:

The responder rate induced in group k ($k = 1, 3, \text{ or } 4$) is NI as compared to the responder rate induced in group R1 using a NI margin of -10%. Similarly, the responder rate induced in group k ($k = 2$) is NI as compared to the responder rate induced in group R2, using a NI margin of -10%

Statistical method:

Objectives 1a and 1b (evaluated at the interim (if conducted) and primary analysis), 1c and 1d (evaluated only at the primary analysis).

To compute the differences in responder rates and associated Agresti-Min confidence intervals, let the dichotomous response post booster and post primary vaccination (reference) summary data be presented in a 2x2 table as follows.

Table 1: Paired Data Study Design Responses

		Post Booster		
Post Primary	Success	Failure	Total	
Success	a	b	a + b	
Failure	c	d	c + d	
Total	a + c	b + d	n	

Where,

- a = Number of participants responding favorably on both the post primary and on the booster
- b = Number of participants responding favorably on the post primary but unfavorably on the booster
- c = Number of participants responding unfavorably on the post primary but favorably on the booster
- d = Number of participants responding unfavorably on both the post primary and on the booster

Let $d = (\hat{P}_{Boost} - \hat{P}_{Primary})$ = Post booster responder rate – Post primary responder rate.

Then,

$$d = \frac{(a + c)}{n} - \frac{(a + b)}{n} = \frac{(c - b)}{n}$$

Based on the data structure given in Table 1, the Agresti-Min (Agresti, A. & Min, Y. (2005).) point estimate and confidence interval (for the population responder difference rates, $\delta = (P_{Boost} - P_{Primary})$) lower and upper bounds are computed as follows:

$$\text{Lower limit} = \frac{(c^* - b^*)}{n^*} - Z_{\alpha/2} \sqrt{\left[(b^* + c^*) - \frac{(c^* - b^*)^2}{n^*} \right] / n^*}$$

$$\text{Upper limit} = \frac{(c^* - b^*)}{n^*} + Z_{\alpha/2} \sqrt{\left[(b^* + c^*) - \frac{(c^* - b^*)^2}{n^*} \right] / n^*}$$

Where $b^* = b + \frac{1}{2}$, $c^* = c + \frac{1}{2}$, and $n^* = n + 2$

For the NI assessment with respect to responder rates, in each group k (k = 1, 3, or 4) compared to the reference group R1 and in group k=2 compared to the reference group R2, the Agresti-Min (Agresti 2005) method, as described above, will be used to estimate the “within-participant” responder rate differences (i.e., booster vaccination after Ad26.COV2.S (original virus or leading variant of high consequence or concern*) minus primary vaccination (original strain or leading variant of high consequence or concern*) and its associated 2-sided $100 * (1 - 2 * \alpha)\%$ CI (where α = 1-sided significance level). This method was chosen because of its well-behaved Coverage Probability (CP) properties compared to other methods for the analysis of matched pairs data (Reed

2009). Coverage probability is generally used to evaluate $(1 - \alpha)$ CIs where α is the Type I error rate.

If an interim analysis is done (objectives 1a and 1b) with alpha spent = 0.0003 (1-sided) at the interim, based on the O'Brien-Fleming group sequential method assuming information fraction of 1/3, then the Agresti-Min method will result in the estimated responder rate difference and associated CI of 99.94% at the Interim analysis and 95.02% (for alpha=0.0249 (1-sided)) at the primary analysis, respectively. If at the time of the interim analysis, the assumption of 1/3 for information fraction is found not to be true, then the O'Brien-Fleming adjustments will be recalculated.

The estimated responder rate difference and associated 97.5% CI for Objectives 1c and 1d will be evaluated only at the primary analysis.

Remark: If no interim analysis is carried out, then the Agresti-Min method will result in the estimated responder rate difference and its 95% CI (objectives 1a and 1b) and 97.5% CI (objectives 1c and 1d) at the PA, respectively.

Success Criterion 2:

Note: success criterion 2 will only be tested if success criterion 1 was met successfully for the hypothesis under consideration.

The GMT induced in group k ($k = 1, 3, \text{ or } 4$) is NI as compared to the GMT induced in group R1 using a NI margin of 2/3. Similarly, the GMT induced in group k ($k = 2$) is NI as compared to the GMT induced in group R2 using a NI margin of 2/3

Statistical method:

Objectives 1a and 1b (evaluated at the interim and primary analysis), 1c and 1d (evaluated only at the primary analysis)

The NI analysis on the GMR, in each group k ($k = 1, 3, \text{ or } 4$) compared to the reference group R1 and in group $k=2$ compared to the reference group R2 , will, respectively, use a paired t-test to estimate the within participant mean differences (i.e., booster vaccination after Ad26.COV2.S (original virus or leading variant of high consequence or concern*) minus primary vaccination (original strain or leading variant of high consequence or concern*) log10 transformed data, or equivalently change from primary on log10 transformed data) and its associated $100 * (1 - 2 * \alpha)\%$ CI (where $\alpha = 1$ -sided significance level). The estimated differences and its CIs will be back transformed to yield the GMR and its associated CI.

Similarly, if an interim analysis is done (objectives 1a and 1b) with alpha spent = 0.0003 (1-sided) at the interim, based on the O'Brien-Fleming group sequential method assuming information fraction of 1/3, then the back transformation of the log10 transformed data, will result in the

estimated GMR difference and associated 99.94% CI at the Interim analysis and 95.02% (for alpha=0.0249 (1-sided)) at the primary analysis, respectively. If at the time of the interim analysis, the assumption of 1/3 for information fraction is found not to be true, then the O'Brien-Fleming adjustments will be recalculated.

The estimated GMR difference and associated 97.5% CI for Objectives 1c and 1d will be evaluated only at the primary analysis.

Remark: If no interim analysis is carried out, then the estimated differences and its CIs will be back transformed to yield the GMR and its 95% CI (objectives 1a and 1b) and 97.5% CI (objectives 1c and 1d) at the PA, respectively.

